11.1.8 Impaired Wound Healing

Impaired wound healing has been observed with some antiangiogenic agents. Ramucirumab will not be administered to patients who have undergone major surgery within 28 days prior to randomization or have undergone central venous access device placement within 7 days prior to randomization. Patients with postoperative and other nonhealing wound complications are excluded, as are patients for whom major surgical procedures are planned.

11.1.9 Liver Failure

Any patient who experiences signs of hepatic encephalopathy or other serious signs of liver impairment, such as hepatorenal syndrome, must be permanently discontinued from ramucirumab therapy.

11.2 Pembrolizumab

It may be necessary to perform conditional procedures such as bronchoscopy, endoscopy, or skin photography as part of evaluation of the event. Suggested conditional procedures, as appropriate, can be found in the ECI guidance document.

- **Pneumonitis:**

- For **Grade 2 events**, treat with systemic corticosteroids. When symptoms improve to Grade 1 or less, steroid taper should be started and continued over no less than 4 weeks.
- For **Grade 3-4 events**, immediately treat with intravenous steroids. Administer additional anti-inflammatory measures, as needed.
- Add prophylactic antibiotics for opportunistic infections in the case of prolonged steroid administration.

- **Diarrhea/Colitis:**

[Type here]

[Type here]

[Type here]

Pembrolizumab + Ramucirumab (Ver 2.5, Oct 2024)

Subjects should be carefully monitored for signs and symptoms of enterocolitis (such as diarrhea, abdominal pain, blood or mucus in stool, with or without fever) and of bowel perforation (such as peritoneal signs and ileus).

- All subjects who experience diarrhea/colitis should be advised to drink liberal quantities of clear fluids. If sufficient oral fluid intake is not feasible, fluid and electrolytes should be substituted via IV infusion. For Grade 2 or higher diarrhea, consider GI consultation and endoscopy to confirm or rule out colitis.
 - For **Grade 2 diarrhea/colitis** that persists greater than 3 days, administer oral corticosteroids.
 - For **Grade 3 or 4 diarrhea/colitis** that persists > 1 week, treat with intravenous steroids followed by high dose oral steroids.
 - When symptoms improve to Grade 1 or less, steroid taper should be started and continued over no less than 4 weeks.
- **Type 1 diabetes mellitus (if new onset, including diabetic ketoacidosis [DKA]) or ≥ Grade 3 Hyperglycemia, if associated with ketosis (ketonuria) or metabolic acidosis (DKA)**
 - For **T1DM** or **Grade 3-4 Hyperglycemia**
 - Insulin replacement therapy is recommended for Type I diabetes mellitus and for Grade 3-4 hyperglycemia associated with metabolic acidosis or ketonuria.
 - Evaluate patients with serum glucose and a metabolic panel, urine ketones, glycosylated hemoglobin, and C-peptide.
- **Hypophysitis:**
 - For **Grade 2** events, treat with corticosteroids. When symptoms improve to Grade 1 or less, steroid taper should be started and continued over no less than 4 weeks. Replacement of appropriate hormones may be required as the steroid dose is tapered.
 - For **Grade 3-4** events, treat with an initial dose of IV corticosteroids followed by oral corticosteroids. When symptoms improve to Grade 1 or less, steroid taper should be started and continued over no less than 4 weeks. Replacement of appropriate hormones may be required as the steroid dose is tapered.

[Type here]

[Type here]

[Type here]

- **Hyperthyroidism or Hypothyroidism:**

Thyroid disorders can occur at any time during treatment. Monitor patients for changes in thyroid function (at the start of treatment, periodically during treatment, and as indicated based on clinical evaluation) and for clinical signs and symptoms of thyroid disorders.

- **Grade 2** hyperthyroidism events (and **Grade 2-4** hypothyroidism):
 - In hyperthyroidism, non-selective beta-blockers (e.g. propranolol) are suggested as initial therapy.
 - In hypothyroidism, thyroid hormone replacement therapy, with levothyroxine or liothyronine, is indicated per standard of care.
- **Grade 3-4** hyperthyroidism
 - Treat with an initial dose of IV corticosteroid followed by oral corticosteroids. When symptoms improve to Grade 1 or less, steroid taper should be started and continued over no less than 4 weeks. Replacement of appropriate hormones may be required as the steroid dose is tapered.

- **Hepatic:**

- For **Grade 2** events, monitor liver function tests more frequently until returned to baseline values (consider weekly).
 - Treat with IV or oral corticosteroids
- For **Grade 3-4** events, treat with intravenous corticosteroids for 24 to 48 hours.
- When symptoms improve to Grade 1 or less, a steroid taper should be started and continued over no less than 4 weeks.

- **Renal Failure or Nephritis:**

- For **Grade 2** events, treat with corticosteroids.
- For **Grade 3-4** events, treat with systemic corticosteroids.
- When symptoms improve to Grade 1 or less, steroid taper should be started and continued over no less than 4 weeks.

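### Section 11.2 sets a later steroid trigger for Grade 3–4 diarrhea/colitis (more than 1 week) than for Grade 2 (more than 3 days) and gives no reason

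*Combined protocol and SAP*

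**What the plan says.** The diarrhea/colitis entry in Section 11.2 (Pembrolizumab) has two adjacent steroid bullets.

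- Grade 2 diarrhea/colitis "that persists greater than 3 days, administer oral corticosteroids".
- Grade 3 or 4 diarrhea/colitis "that persists > 1 week, treat with intravenous steroids followed by high dose oral steroids".

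Ahead of these bullets, the entry asks for monitoring for enterocolitis and bowel perforation, and for fluid replacement. It then adds a diagnostic step: "For Grade 2 or higher diarrhea, consider GI consultation and endoscopy to confirm or rule out colitis". None of this carries a waiting period.

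Three other places bear on the point.

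- The dose-modification table in Section 8.4.1 holds pembrolizumab for Grade 2–3 diarrhea/colitis and stops it permanently at Grade 4. It sets no start time for steroids.
- Section 9.2 prohibits systemic glucocorticoids, but excepts their use for symptoms of an event suspected to be immunologic.
- Sections 8.4.1 and 11.2 both refer to a separate guidance document on events of clinical interest. Section 8.4.1 cites it for supportive care, including corticosteroid use.

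**The concern.** A severity-graded rule would normally act at least as soon for the worse grade. Here the days run the other way: the sicker patient reaches the written steroid instruction later. A patient who presents at Grade 3 or 4, or who gets there within the first 3 days, has no steroid instruction in the protocol body until the event has lasted more than a week.

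A waiting period in itself is not the problem. The entry has one at Grade 2 as well, and a diagnostic step is a sensible reason for some delay. The problem is the order of the two periods.

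What is at stake is patient safety. The same entry asks staff to watch for bowel perforation. Section 11.1.5 says that some of these patients may already be at raised risk of perforation because of their gastric cancer, and Section 10.2.5 lists perforation among the adverse events of special interest. The documents do not say how steroid timing affects that risk, so no rate is attached to it here.

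**Working it through.** The plan states no figure to reproduce. The check sets the passages side by side, with one subtraction.

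**1. Inputs (Section 11.2, diarrhea/colitis entry)**

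| Grade | Written trigger | Treatment started |
|---|---|---|
| 2 | more than 3 days | oral corticosteroids |
| 3 or 4 | more than 1 week = more than 7 days | intravenous, then high-dose oral |

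**2. Difference between the triggers.** 7 − 3 = 4 days later at the higher grade. This counts each period from the onset of its own grade. The section does not say when counting starts, so that is an assumption.

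**3. How the assumption matters.** Let d be the days spent at Grade 2 before the event reaches Grade 3.

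- If d is more than 3, the Grade 2 bullet has already called for oral steroids, and the order of the triggers does no harm.
- If d is 3 or less, that bullet has not applied. When the count restarts at Grade 3, the written start falls after d + 7 days from the onset of Grade 2. That is after 0 + 7 = 7 days for a patient who presents at Grade 3–4, and after 3 + 7 = 10 days at most.
- If both periods instead run from the onset of the diarrhea, the triggers fall after day 3 and after day 7. The difference is again 4 days, and the count does not restart.

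The order is the same under each reading. Only the total wait changes.

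**4. Search for a stated reason.** The one candidate in the entry is the step to confirm or rule out colitis. It applies from Grade 2 upward, so it could explain a wait at both grades but not a longer one at Grade 3–4. The Section 8.4.1 table gets stricter with grade (hold at Grade 2–3, stop at Grade 4) and is silent on when steroids begin. No other section addresses the timing.

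**5. Permission against instruction.** Section 9.2 allows steroids for a suspected immune event with no time limit. That is an exception to a prohibition; it does not direct anyone to treat. The only Grade 3–4 start that the protocol body instructs is the one after a week.

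**6. Number of patients.** This cannot be computed. Section 12 plans at most 26 patients (Section 7.1 says 35), and the documents give no rate of diarrhea or colitis.

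**The case against.** The strongest reply is that little turns on this bullet in practice. Pembrolizumab is already held or stopped at these grades. Monitoring, fluids and consideration of endoscopy start at once. Earlier steroids are permitted by Section 9.2, and Section 10.2.1 makes the treating physician responsible for appropriate care. The Section 8.4.1 row for Grade 2–3 diarrhea/colitis makes failure to reduce corticosteroids a ground for discontinuation, so it presupposes steroid use at Grade 3 and states no wait. The external guidance may also give an earlier start.

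Most of this stands, and it narrows the exposure. It does not remove the reversed order: these provisions allow earlier treatment without instructing it, and guidance that is not among the documents cannot be assumed to cure the text. If that guidance does say something earlier, the protocol body disagrees with it and still needs correcting.

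Two stronger readings are tempting and are not supported.

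- A reader might infer that the protocol makes patients with severe colitis go a week without steroids. It does not: nothing forbids earlier use for a suspected immune event.
- A reader might also argue that the other toxicity entries in Section 11.2 prove a pattern that this one breaks. They are weak evidence. Grade 3–4 pneumonitis does state a time ("immediately treat with intravenous steroids"), but most of the other bullets give no timing, and silence is not the same as a wait of zero days. The point rests on the two diarrhea/colitis bullets alone.

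**Conclusion.** The point holds as a defect in the written safety guidance. The steroid trigger for diarrhea/colitis is later at Grade 3–4 than at Grade 2, by 4 days if each period is counted from the onset of its own grade, and the protocol gives no reason.

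It affects only patients who are at Grade 3–4 before the Grade 2 trigger is met and whose physician follows the bullet to the letter. How many that would be is unknown. Whether the external guidance explains or overrides the timing is also unknown, so the conclusion is limited to the protocol text.

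This is a clinical management point. The ORR estimate, the two-stage sample size and the error rates do not depend on it. It deserves correction because it concerns patient safety and one bullet settles it.

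**What to change.** Replace the Grade 3–4 bullet with wording to this effect: *For Grade 3 or 4 diarrhea/colitis confirmed or suspected to be immune-related, start intravenous steroids, then high-dose oral steroids, promptly and no later than the Grade 2 trigger (> 3 days), unless work-up has established a non-immune cause.* It would help to say in the same place from when the days are counted.

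The condition on cause matters. A rule requiring steroids after 3 days whatever the work-up showed would conflict with Section 9.2, which restricts systemic glucocorticoids to suspected immune events and calls for removal of subjects who need a prohibited treatment.

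If the later Grade 3–4 trigger is intended, state the reason in Section 11.2 instead.

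Cost: one bullet. On the same counting assumption, the latest written start for a confirmed or suspected immune-related Grade 3–4 event moves from after day 7 to the Grade 2 trigger at day 3. The downside is that some patients may start steroids before work-up is complete. Visits, sample size and analyses do not change.

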12. SAMPLE SIZE

Sample Size Calculation

[Type here]

[Type here]

[Type here]

Pembrolizumab + Ramucirumab(Ver 2.5, Oct 2024)

A maximum of 26 patients will be recruited to this single-arm phase II trial. The primary endpoint of this trial is overall response (OR=PR+CR).

In this single-arm phase II trial, 25 people were calculated using Simon's two-stage design and a total of 26 patients will be recruited to account for a 5% dropout rate.

The sample size is calculated by use of a two-stage minimax Simon's design to control the type I error at 5 % for null hypothesis that, for arm, the true response was 15 % or below and to have 85 % of power if the true response was 40 % or higher. 15 evaluable patients are to be treated in the first stage. If 1 or fewer response are observed in the first stage, the arm will be stopped. If at least 2 responses are observed in the first stage, 10 additional evaluable patients are to be entered onto the second stage. At the final analysis, the null hypothesis will be rejected if at least 7 responses are observed in 25 evaluable patients. RR is reported with its exact 95% CI.

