--	--

[Type here]

[Type here]

[Type here]

Pembrolizumab + Ramucirumab (Ver 2.5, Oct 2024)

	
is detected). Chronic HBV infection with anti-viral agent prophylaxis is allowed.
 
22. Has known liver cirrhosis at a level of Child-Pugh B (or worse) or cirrhosis (any degree) and a history of hepatic encephalopathy or clinically meaningful ascites resulting from cirrhosis. Clinically meaningful ascites is defined as ascites from cirrhosis requiring diuretics or paracentesis.
 
23. The patient is pregnant or breastfeeding

Goal:	To estimate efficacy and safety of combination therapy of Ramucirumab and Pembrolizumab in patients with metastatic gastric or GEJ adenocarcinoma
Planned Sample Size:	
: A maximum of 26 patients (considering 5% drop out rate) will be recruited to this single-arm phase II trial.
 
In this single-arm phase II trial, 25 people were calculated using Simon's two-stage design and a total of 26 patients will be recruited to account for a 5% dropout rate. The sample size is calculated by use of a two-stage minimax Simon's design to control the type I error at 5 % for null hypothesis that, for arm, the true response was 15 % or below and to have 85 % of power if the true response was 40 % or higher. 15 evaluable patients are to be treated in the first stage. If 1 or fewer response are observed in the first stage, the arm will be stopped. If at least 2 responses are observed in the first stage, 10 additional evaluable patients are to be entered onto the second stage. At the final analysis, the null hypothesis will be rejected if at least 7 responses are observed in 25 evaluable patients. RR is reported with its exact 95% CI.

Duration of Study:	Until 100% enrollment from approval regulatory authority
Study design (Dosage & Treatment):	
Patients will continue to receive study treatment, until they demonstrate objective disease progression (determined by modified RECIST 1.1) or until they meet any other discontinuation criteria.
 
 - Ramucirumab 8mg/kg on q2W - Pembrolizumab 200mg on q3W (pembrolizumab first followed by ramucirumab when concurrently administered on the same day)

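### Minor: a maximum of 26 patients covers one loss (3.8%), not the stated 5% dropout from 25 evaluable, and no final decision rule is given for any number other than 25

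*Combined protocol and SAP*

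**What the plan says.** Section 12 describes a two-stage Simon design meant to "control the type I error at 5" percent when "the true response was 15 % or below", with "85 % of power if the true response was 40 % or higher". On stage 1 it says "15 evaluable patients are to be treated in the first stage" and "If 1 or fewer response are observed in the first stage, the arm will be stopped". Ten more evaluable patients follow in stage 2. The final rule is that "the null hypothesis will be rejected if at least 7 responses are observed in 25 evaluable patients".

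On recruitment, Section 12 says that "a total of 26 patients will be recruited to account for a 5% dropout rate" and calls 26 a maximum. The synopsis (Planned Sample Size) agrees: "A maximum of 26 patients (considering 5% drop out rate) will be recruited".

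Two other places bear on this. Section 7.1 gives the maximum as 35 patients. Section 13.1.1 divides the responders by an ITT population made up of everyone who received at least one dose, not by the evaluable patients. Neither Section 12 nor the synopsis defines an evaluable patient, provides for replacement, or says what happens if the final number is not 25.

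**The concern.** A required minimum inflated for loss is normally rounded up. Here 26.3 was rounded down to 26 and then fixed as a maximum, so the number does not deliver the allowance attached to it.

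Beyond the slip, the only final rule is written for 25 patients. With two or more non-evaluable patients the number is 24 or fewer. If everyone is dosed and the ITT denominator is used, it is 26. In an open-label, single-arm trial, a cut chosen at that point would be chosen with the responses already known.

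**Working it through.** **Inputs.** From Section 12 and the synopsis: 25 evaluable patients, 5% dropout, 26 recruited; null rate 15%, alternative 40%; 15 patients in stage 1, stop at 1 or fewer responses; reject at 7 or more. Assumptions, because the plan is silent: losses are independent, and the test is one-sided as in a Simon design.

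**1. The plan's figure.** 25/0.95 = 26.32, and the cruder 25 × 1.05 = 26.25. Both give 26 to the nearest whole number, which is presumably how 26 arose, and both give 27 when rounded up.

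**2. What 26 delivers.** Expected evaluable: 26 × 0.95 = 24.7. Losses allowed while keeping 25: 26 − 25 = 1, and 1/26 = 3.8%.

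**3. Chance of fewer than 25 evaluable, if dropouts are not evaluable and all recruits are enrolled.**

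- 26 recruited: P(0 losses) = 0.95^26 = 0.2635; P(1 loss) = 26 × 0.05 × 0.95^25 = 0.3606. Shortfall = 1 − 0.6241 = **37.6%**.
- 27 recruited: **15.0%**. 28 recruited: 4.9%.
- 26 recruited with 3% or 10% dropout instead of 5%: 18% or 75%.

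The 37.6% also presumes that stage 2 opens. The chance of 2 or more responses in 15 is 0.681 at a 15% response rate and 0.995 at 40%. Treating dropout as independent of response, the unconditional figures are 0.681 × 0.376 = 26% and 0.995 × 0.376 = 37%.

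**4. The same question under Section 13.1.1.** A patient who drops out after a first dose stays in the denominator; only a patient never dosed leaves it. If all losses follow dosing, the shortfall probability is about 0% and the denominator is 26. If all precede dosing, it is 37.6%. The plan does not say when dropout occurs, so it could be anywhere between.

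**5. The stated rule at nearby final numbers.** For final number n,

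P(reject) = Σ over x = 2,…,15 of P(Bin(15, p) = x) × P(Bin(n − 15, p) ≥ 7 − x),

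with p = 0.15 for type I error and p = 0.40 for power:

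| Final n | Type I error, cut 7 | Power, cut 7 |
|---|---|---|
| 23 | 4.6% | 87.6% |
| 24 | 5.7% | 90.4% |
| 25 | 6.9% | 92.6% |
| 26 | 8.3% | 94.3% |

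**6. Averaged over 5% loss.** Weighting the power at each n (analysing no more than 25) by its binomial probability gives 91.2% with 26 recruited and 92.1% with 27. Power first falls below 85% at n = 22, where it is 84.1%. Four or more losses in 26 has probability 3.9%.

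**The case against.** A reader might infer that the rounding makes the trial miss its analysis size about 38% of the time, and that this harms the primary analysis. The documents do not support that, for four reasons.

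- **The rounding does not cause the whole 37.6%.** Inflating for dropout targets the expected number and guarantees nothing. The correctly rounded 27 still falls short 15.0% of the time.
- **The figure is conditional.** It needs dropouts to be non-evaluable and all 26 to be enrolled. Section 13.1.1 keeps dosed dropouts in the response-rate denominator, which could bring the figure to about zero.
- **The cap is itself in doubt.** Section 7.1 allows 35, which would cover 5% loss. One cannot say flatly that a second loss is irreplaceable while the documents disagree.
- **The consequence is mild.** With the cut kept at 7, power at 24 or 23 patients stays above the stated 85%, and type I error falls towards the stated 5%.

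All four points stand, and they make this a minor correction. They do not remove it. Section 12 and the synopsis both tie the 5% allowance to 26, so the sentence remains untrue on its own terms. The 35 is a contradiction to resolve, not a provision for dropout. The ITT reading does not rescue the rule either: with all 26 dosed, the denominator is again a number for which no cut is stated.

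**Conclusion.** The point holds as a minor error. The stated allowance is short by one patient on strict rounding: 26 covers 3.8% loss, not 5%. The chance of fewer than 25 is 37.6% on the evaluable-patient reading with full enrolment and independent 5% loss, and between about 0% and 38% on the ITT reading.

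The power cost is about 1.4 points on average (92.6% to 91.2%). That small cost depends on keeping the cut at 7, whose error is 6.9% at the planned 25, above the stated 5%. That excess is a separate matter and adds no weight here, but it is where the spare power comes from. If the cut were moved to 8, which the plan does not propose, power would be 84.6% at 25 and 80.8% at 24, and a lost patient would matter more.

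The more useful part of the correction is the missing rule. A final number of 24 or 26 is quite possible under the plan's own figures, and the primary decision is undefined at both.

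**What to change.** In Section 12 and the synopsis:

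1. Replace the dropout sentence with one that the numbers support, for example: *26 patients allows for one non-evaluable patient (3.8%).* If the sponsor prefers to keep 5%, the matching number is 27.
2. Reconcile the maximum of 26 with the 35 in Section 7.1.
3. Define an evaluable patient and reconcile that count with the ITT denominator in Section 13.1.1, stating which one the decision rule uses.
4. State the rejection count with its exact error and power for final numbers 23 to 26, fixed before the final data are seen. The table above gives these for a cut of 7; it must be recomputed if the cut changes.

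The cost is one reworded sentence, one definition, one reconciled number and a four-row table. No extra patients are needed if the allowance is restated as 3.8%; the only price is a slightly less generous stated allowance.

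### The stated two-stage rule (stop if 1 or fewer of 15; reject at 7 or more of 25) has an exact type I error of 6.9% and power of 92.6%, not the stated 5% and 85%, and is not the minimax design

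*Combined protocol and SAP*

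**What the plan says.** Section 12 names the design and its error rate: "The sample size is calculated by use of a two-stage minimax Simon's design to control the type I error at 5"%. The null hypothesis is that "the true response was 15 % or below", and the design is meant "to have 85 % of power if the true response was 40 % or higher". For the first stage, "15 evaluable patients are to be treated in the first stage"; the arm stops at 1 or fewer responses and otherwise takes in 10 more patients. The final rule is: "At the final analysis, the null hypothesis will be rejected if at least 7 responses are observed in 25 evaluable patients".

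The Planned Sample Size entry of the synopsis repeats the same design, including the final rule ("the null hypothesis will be rejected if at least 7 responses are observed in 25 evaluable patients"). Neither place reports the achieved type I error or power of the rule, and nothing elsewhere in the document allows a type I error above 5%.

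**The concern.** A Simon design is fixed by four integers: the first-stage size, the first-stage bound, the total size and the final cut-off. Given these, type I error and power are exact binomial quantities and should meet the stated targets. Here the integers and the targets appear together but do not match.

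This rule is the only hypothesis test in the plan. If its error rate is misstated, a result of 7 of 25 (28%) would be reported as a rejection of 15% at the 5% level when the procedure carries a higher false-positive risk. A reader would also be told that the sample size came from a minimax search that does not return these numbers.

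**Working it through.** **Inputs** (all from Section 12, repeated in the synopsis): p0 = 0.15; p1 = 0.40; target type I error 0.05; target power 0.85; n1 = 15; stop if X1 ≤ 1; n2 = 10, so n = 25; reject if X1 + X2 ≥ 7.

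**Formula.** With X1 ~ Bin(15, p) and X2 ~ Bin(10, p), and k the final cut-off,

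P(reject | p) = Σ over x = 2,…,15 of P(X1 = x) × P(X2 ≥ k − x),

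where the second factor is 1 once x ≥ k.

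**Type I error as written** (p = 0.15, k = 7):

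| x in stage 1 | P(X1 = x) | P(X2 ≥ 7 − x) | product |
|---|---|---|---|
| 2 | 0.2856 | 0.0099 | 0.0028 |
| 3 | 0.2184 | 0.0500 | 0.0109 |
| 4 | 0.1156 | 0.1798 | 0.0208 |
| 5 | 0.0449 | 0.4557 | 0.0205 |
| 6 | 0.0132 | 0.8031 | 0.0106 |
| 7 or more | 0.0036 | 1 | 0.0036 |

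The sum is 0.0692. The stated 5% is not reproduced; the ratio is 0.0692/0.05 = 1.38.

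**Power as written** (p = 0.40, k = 7): the same sum gives 0.9256. The stated 85% is not reproduced; the gap is 92.6 − 85 = 7.6 percentage points.

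**Can another reading rescue the 5%?**

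- Ignoring the first-stage stop gives P(Bin(25, 0.15) ≥ 7) = 0.0695, so how the interim look is treated hardly matters.
- The 6.9% is already a single upper tail. Reading the 5% as two-sided would allow only 2.5% in that tail and widen the gap.
- The rule reaches 5% only if the null rate is about 14.0% rather than 15%.

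**Alternatives, by the same formula:**

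| Stage 1: stop if | Final: reject if | Type I error | Power |
|---|---|---|---|
| ≤ 1 of 15 (as stated) | ≥ 7 of 25 (as stated) | 0.0692 | 0.9256 |
| ≤ 1 of 15 | ≥ 8 of 25 | 0.0254 | 0.8462 |
| ≤ 3 of 15 | ≥ 7 of 25 | 0.0555 | 0.8784 |
| ≤ 4 of 15 | ≥ 7 of 25 | 0.0347 | 0.7729 |
| ≤ 3 of 14 | ≥ 7 of 25 | 0.0499 | 0.8503 |
| ≤ 4 of 17 | ≥ 7 of 25 | 0.0484 | 0.8562 |
| ≤ 1 of 10 | ≥ 7 of 23 | 0.0434 | 0.8575 |

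The last row is what an exhaustive search returns as the minimax design for 15% against 40%, 5% and 85%. Its total is 23, so a 25-patient design is not minimax for these inputs. The rows with 14 and 17 patients in stage 1 show that 7 of 25 can meet both targets, but not with the stated first stage.

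**Exact (Clopper–Pearson) intervals at the boundary:** for 7/25 the 95% interval is 12.1% to 49.4% and the 90% interval 13.9% to 46.2%. For 8/25 the 95% interval is 14.95% to 53.5% and the 90% interval 17.0% to 50.4%.

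**The case against.** The strongest reply is about consequence. The primary objective is to estimate a preliminary response rate, Section 13.1.1 specifies only an estimate with a confidence interval, and the excess is 1.9 percentage points in a trial of at most 26 patients. That limits the practical weight. It does not make the statement correct: the synopsis and Section 12 set out a null hypothesis, an error rate and a rejection rule, and these three do not fit together.

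Three stronger readings are tempting but not supported.

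- A reader might infer that the cut-off is simply one response too low, perhaps because 7 was meant as the largest count that does not reject. Power would then be 84.6%, close to 85%, so this is plausible. The documents do not say it; the slip could equally be in the first-stage bound, the stage sizes or the inputs.
- A reader might infer that a cut-off of 7 belongs with 23 patients and cannot go with 25. It can: stopping at 3 or fewer of 14 and rejecting at 7 of 25 meets both targets.
- A reader might take the 95% interval at 7/25, which includes 15%, as proof that the rule is wrong. The 95% interval at 8/25 starts at 14.95% and includes 15% too. A one-sided 5% test and a two-sided 95% interval need not agree even in a correct design, so this does not separate 7 from 8.

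**Conclusion.** The point stands as an error in the plan's stated operating characteristics. The rule as written has an exact one-sided type I error of 6.9% against the stated 5%, and power of 92.6% against the stated 85%. It is not the minimax design for the stated inputs. The 7 of 25 rule fails in combination with the stated first stage; which element is the slip cannot be settled from the documents.

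The figures assume independent responses with a common response probability, exactly 15 and then 10 evaluable patients, and binding application of the first-stage stop. The last assumption matters little (6.9% against 6.95%).

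**What to change.** Make the same correction in the synopsis (Planned Sample Size) and in Section 12, choosing one of:

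1. Change the final rule to at least 8 responses in 25, and state a type I error of 2.5% and power of 84.6%.
2. Keep at least 7 in 25, state a type I error of 6.9% and power of 92.6%, and remove the claim of 5% control.

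Delete the word minimax in either case. The first-stage rule need not change to correct this error.

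The documents do not say how far enrolment has gone. If response data have already been seen, take option 2, or date the change of threshold and justify it on grounds independent of those data.

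Optionally, report an exact 90% interval beside the planned 95% interval, so that one of the two matches a one-sided 5% test.

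No extra patients are needed. Option 1 costs one more response for success and leaves power 0.4 points below 85%; option 2 costs a less favourable stated error rate.
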